3.2. SCHEDULE OF EVENTS

The schedule of events for the 24-week, double-blind, treatment period can be found below, and in Section 11.3 of the study protocol.

Assessment	Visit	Screening	Baseline ^A	Day 1	Day 2	Day 7	Day 14	Day 15	Week 8	Week 16	Final (Week 24) ^H	Safety follow-up ^J
	Study day(s)	-28 to -1	0	1	2	3-7	8-14	15	16-56	57-112	113-168	169-182
Informed consent (before any study procedure)		X										
Inclusion/Exclusion Criteria		X	X									
Demography/Background Information		X										
MECP2 gene mutation confirmation		X ^P										
Medical History and Current Medical Conditions		X										
Vital Signs		X	X ^C	X ^C	X		X	X	X	X	X	X
ECG (12-lead)		X	X ^D	X ^D	X		X	X	X	X	X	
Physical Examination		X	X ^B		X		X		X	X	X	
Neurological Examination		X	X ^B		X		X		X	X	X	
Ophthalmological Examination			X							X	X	
Laboratory Evaluation (Hematology, Biochemistry, Urinalysis)		X	X ^B				X		X	X	X	
Thyroid Function Tests (TSH, T3, T4)		X										
Virology (Hepatitis B/C, HIV)		X										
Plasma ACTH and cortisol			X		X					X	X	
Serum prolactin			X							X	X	
Serum pregnancy test ^O		X	X								X	
Tanner Staging			X								X	
Suicidality assessment			X						X		X	
Dosage administration and drug label record				X	X	X	X	X	X	X	X ^K	

Document: \\ieedc-vnasc01\BIOSdata\Newron\Sarizotan\PXA76395\Biostatistics\Documentation\SAP
 Author: [name] Version Number: V2
 Version Date: [30March2020]

Template No: CS_TP_BS016 – Revision 4
 Effective Date: 01Apr2016

Reference: CS_WI_BS005

Assessment	Visit	Screening	Baseline ^A	Day 1	Day 2	Day 7	Day 14	Day 15	Week 8	Week 16	Final (Week 24) ^H	Safety follow-up ^J
Prior/Concomitant Medications and Significant Non-Drug Therapies		X	X	X	X	X	X	X	X	X	X	
Adverse Events		X	X	X	X	X	X	X	X	X	X ^E	X
Respiratory monitoring (in clinic) ^M			X							X	X	
Respiratory monitoring (at home) ^N		X					X		X	X	X	
CGI-C							X		X	X	X	
CIC							X		X	X	X	
RCSS			X								X	
Motor-Behavioral Assessment Scale			X						X	X	X	
Caregiver Top 3 Concerns			X						X	X	X	
Telephone contact ^G						X						
Pharmacokinetic blood sample				X ^F				X ^F				
Overnight stay (hotel/housing) required			X	X	X ^L		X	X ^L				
Study Completion											X ^I	X

^A Patients meeting all entry criteria will report to the hospital/clinic on Day 0. Baseline evaluations may be started on Day 0 and continued on Day 1 pre-dose. Following completion of baseline evaluations, subjects will be randomized and dosed on Day 1.

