6.1. REFERENCE START DATE AND STUDY DAY

Study Day will be calculated from the reference start date, and will be used to show start/stop day of assessments and events.

Reference start date is defined as the day of the first dose of study medication (Day 1 is the day of the first dose of study medication), and will appear in every listing where an assessment date or event date appears.

If the date of the event is on or after the reference start date then:

Study Day = (date of event – reference start date) + 1.

If the date of the event is prior to the reference start date then:

Study Day = (date of event – reference start date).

In the situation where the event date is partial or missing, the date will appear partial or missing in the listings, and Study Day, and any corresponding durations will be presented based on the imputations specified in Appendix 1; Partial Date Conventions.

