6.2. BASELINE

Unless otherwise specified, baseline is defined as the last non-missing measurement taken prior to reference start date (including unscheduled assessments). In the case where the last non-missing measurement and the reference start date coincide, that measurement will be considered pre-baseline, but Adverse Events (AEs) and medications commencing on the reference start date will be considered post-baseline.

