8.1. DATA SELECTION FOR DOUBLE BLIND TREATMENT PERIOD (24 WEEKS)

For patients who enter the open-label extension treatment period, all data up to and including the date of the first dose in the open-label extension phase will be considered as part of the double-blind treatment period (24 weeks). For patients who do not enter the open-label extension, all data will be included in the double-blind treatment period (24 weeks).

8.2. VISIT WINDOWS:

The following visit windows will be used for analyses of efficacy endpoints:

Visit	Window
Screening (day - 28)	Day - ∞ to day -1
Baseline (day 0)	Day -28 to day 0 (last value before first dose of study drug) [Baseline for the BioRadio™ data will be the last value prior to Day 1 (no cutoff at Day -28)]
Day 1	No window (day of the first dose taken)
Day 2	No window (immediately after day 1)
Week 2 (day 14)	Day 1 to day 35
Day 15	No window (immediately after day 14)
Week 8 (day 56)	Day 36 to day 84
Week 16 (day 112)	Day 85 to day 140
Week 24 (day 168)	Day 141 to day 196
Safety follow - up	Day 1 – Day 30 where Day 0 Is the day when the patient discontinues the study. This Is likely to be a scheduled visit day – but possibly an unscheduled visit. Operationally it might be identified by being the previous day that a vital sign was measured (or any other measurement that is done when a patient either reaches Week 24 or discontinues prematurely – as per the protocol schedule of evaluations). Importantly the patient is no longer on drug during this entire window.

Note: Day 1 = first dosing day of study drug

Document:	\\iecdc-vnasc01\BIOSdata\Newron\Sarizotan\PXA76395\Biostatistics\Documentation\SAP	Version Number:	V2
Author:	[name]	Version Date:	[30March2020]

Template No: CS_TP_BS016 – Revision 4
 Effective Date: 01Apr2016

Reference: CS_WI_BS005

If there is more than one record within the same window, the non-missing value closest to the scheduled visit study day will be used for analyses. If two values are equidistant from the scheduled visit day, the earliest non-missing value will be used.

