15.2.1.3 Change from baseline to Week 24 in Motor-Behavioral Assessment Scale (MBAS)

The MBAS is comprised of three sub-scales i.e. Behavioral/Social Assessment (included 16 items), Orofacial/Respiratory Assessment (included 7 items) and Motor Assessment/Physical Signs (included 14 items).

Each item is rated on a scale from 0 to 4, with '0' indicating normal or never, and '4' indicating very severe or constant.

To see the change in Motor-Behavioral Assessment Scale, change from baseline will be calculated at Week 24, considering the grand total score (all 3 sub-scales), as well as the total score on each of the three sub-scales.

Day 0 will be considered as baseline for this endpoint.

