15.2.2 MISSING DATA METHODS FOR SECONDARY EFFICACY VARIABLES

Last observation carried forward (LOCF) method will be adopted as imputation in the presence of at least one post-baseline observation if data is collected at multiple visits post baseline and is missing. Missing items in, Top 3 concerns score at baseline will be imputed with the mean baseline value of that item of all patients in the analysis population. There will be no imputation for MBAS, RCSS and Other Respiratory symptoms of RTT since only descriptive summary is presented.

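### SAP 8.2's day limits conflict with its own wording and with SAP 6.2 on a Caregiver Top 3 Concerns baseline rated on Day 1 before dosing

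*SAP*

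**What the plan says.** Footnote A of the schedule (SAP 3.2; also Protocol 11.3) states: "Baseline evaluations may be started on Day 0 and continued on Day 1 pre-dose". Protocol 11.4.2 defines the Baseline visit over the same span and lists the Caregiver Top 3 Concerns within it. The narrative in Protocol 11.2 puts the baseline efficacy ratings on Day 0, so a Day 1 rating is permitted but is not the default.

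SAP 6.1 derives study day from dates alone. On or after the first dose the rule is "Study Day = (date of event – reference start date) + 1", and for earlier dates the 1 is not added.

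SAP 8.2 gives the Baseline window as "Day -28 to day 0 (last value before first dose of study drug" and the Week 2 window as study days 1 to 35, with the footnote "Note: Day 1 = first dosing day of study drug". BioRadio data have their own baseline rule in the same row.

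SAP 6.2 states the general rule: "Unless otherwise specified, baseline is defined as the last non-missing measurement taken prior to reference start date". It adds that when the last measurement falls on the reference start date it is treated as pre-baseline. SAP 6.3 says that the analysis windows decide the visit under which data are reported.

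Under SAP 15.2.2, a missing item in the Top 3 Concerns "score at baseline will be imputed with the mean baseline value of that item of all patients in the analysis population". LOCF applies once there is at least one post-baseline observation.

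**The concern.** One permitted record has two possible places in the analysis. Two programmers, one working from the day limits in SAP 8.2 and the other from its bracketed words and SAP 6.2, would derive different baselines for the same patient.

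The endpoint is the Top 3 Concerns Total Score, which stands third in the confirmatory sequence (SAP 7.4) and is analysed by ANCOVA with baseline as a covariate. On the day-number reading, a patient who has a valid pre-dose rating loses it as a covariate and receives cohort means. The rating itself becomes the only Week 2 value, because no Top 3 Concerns rating is scheduled at Week 2.

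**Working it through.** The plan gives no figure on this point to reproduce. The check has four steps.

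**1. Where the record falls by day number**

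| Date of rating | Study day (SAP 6.1) | SAP 8.2 window by number |
|---|---|---|
| Day before first dose | −1 | Baseline (also Screening) |
| Day of first dose, before dosing | 0 + 1 = 1 | Week 2 only |
| Day after first dose | 1 + 1 = 2 | Week 2 |

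The formula uses dates, so pre-dose and post-dose records on the dosing date are both study day 1. It never returns 0.

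**2. When the pre-dose rating would be carried forward**

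Patients who stop early are to have all Week 24 assessments (Protocol 9.2.4; footnote H), and these include the Top 3 Concerns. SAP 8.2 keeps the value closest to the scheduled day, or the earlier one on a tie. Day 1 is 14 − 1 = 13 days from Day 14.

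- Discontinuation rating on Days 2 to 26: at most 12 days from Day 14, so it displaces the Day 1 value.
- Day 27: 13 days away, a tie, so Day 1 is kept.
- Days 28 to 35: 14 to 21 days away, so Day 1 is kept.
- Days 36 to 84: Week 8 window, so the later rating is the one carried forward.

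The pre-dose value is therefore carried to Week 24 only if there is no later rating at all, or if the only later rating falls on Days 27 to 35.

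**3. Loss of precision with no early dropout**

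Let p be the share rated on Day 1, r the baseline to Week 24 correlation and σ² the outcome variance. I treat an imputed total as one cohort mean. Residual variance is σ²(1−r²) for patients with their own baseline and σ² for imputed patients. The average is

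σ²[(1−p)(1−r²) + p] = σ²(1−r²)·[1 + p·r²/(1−r²)].

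| p | r = 0.5 (factor 0.25/0.75 = 0.333) | r = 0.7 (factor 0.49/0.51 = 0.961) |
|---|---|---|
| 0 | 0% | 0% |
| 10% | 3% | 10% |
| 25% | 8% | 24% |
| 50% | 17% | 48% |

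A simulation (43 per arm, SD 50, r = 0.6, true difference −20, 3,000 runs) gives the same picture. The estimate stays near −20. Its SD is 8.52 with correct baselines, and 8.73, 9.07, 9.35 and 9.67 at p = 5%, 10%, 25% and 50%. The squared ratios to 8.52 are 1.05, 1.13, 1.20 and 1.29. The formula, with factor 0.36/0.64 = 0.5625, gives 1.03, 1.06, 1.14 and 1.28. Each simulated ratio has a Monte Carlo error of about 0.04 (relative error √2·√(2/3000) ≈ 0.037), and all four share one denominator.

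**4. Dilution if the pre-dose value is carried forward**

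Worst case: a share e leaves before Week 8 with no discontinuation rating. Leavers rated on Day 1 then enter the analysis with a pre-treatment value; other leavers have no post-baseline value and drop out. The share of analysed patients carrying no treatment effect is p·e/[1 − e(1−p)].

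- e = 10%, p = 25%: 0.025/0.925 = 2.7%, so −20 becomes about −19.5.
- e = 10%, p = 50%: 0.05/0.95 = 5.3%, so −20 becomes about −18.9.

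The simulation gives −19.48 (SD 9.58) and −18.99 (SD 10.28), against −20.11 (SD 9.16) with the baseline correctly assigned.

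The SD, p, r, e and the true difference are assumptions. None is in the documents.

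**The case against.** The strongest reply is that the SAP already gives the sensible answer. The Baseline row itself refers to the last value before the first dose, which a Day 1 pre-dose form satisfies. SAP 6.2 addresses the same-date case and calls it pre-baseline. SAP 8.2 also has a separate Day 1 row, which suggests that the authors did not think of the dosing day as Week 2. A completed form is not a missing item, so the imputation rule would never be triggered.

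Most of this stands, and it rules out three stronger readings that a reader might draw.

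- *The SAP directs that the baseline be replaced.* It does not. Replacement follows only from applying the day limits and ignoring the bracketed words and SAP 6.2.
- *Anyone leaving before Week 8 has a pre-treatment value carried to Week 24.* The discontinuation rating prevents this outside the narrow cases in step 2.
- *MBAS and RCSS changes are lost.* SAP 15.2.1.3 says "Day 0 will be considered as baseline for this endpoint", and 15.2.1.5 uses the same rule. The study-day formula yields no Day 0, but SAP 8 and 8.2 use Day 0 as the name of the Baseline visit, and read that way the rule works. Both scales are only described, without imputation.

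The reply does not settle which text governs. SAP 6.2 gives way where something else is specified, and 8.2 specifies windows for efficacy endpoints. The term in 6.2 is pre-baseline, not baseline. SAP 6.3 gives the windows authority over the visit. The BioRadio exemption from the Day −28 limit implies that the limits bind elsewhere. The Week 2 row has no pre-dose exclusion, and its range overlaps the Day 1 row.

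**Conclusion.** The contradiction is real but minor. SAP 8.2 disagrees with itself and with SAP 6.2 about a record that the schedule permits, and the difference reaches one inferential analysis, the third test in the sequence.

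If the windows are programmed by day number, the main effect is lost precision: about 3% to 17% more ANCOVA variance at r = 0.5 for p of 10% to 50%, more at a higher correlation, and none if every form was completed before the dosing date. A slight dilution is added only where early leavers lack a usable discontinuation rating. With no early dropout the simulated estimate stays near the true value.

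The primary endpoint has its own baseline rule, CIC has no baseline rating, and the win criteria (SAP 15.1.4) do not use the Top 3 Concerns. The size rests on p and r, which the documents do not give.

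**What to change.** In SAP 8.2, define Baseline for everything except BioRadio as the last value before the first dose, including Day 1 pre-dose values identified by clock time or by the nominal Baseline visit. Start the Week 2 window on Day 2 so that it holds only post-dose records. This agrees with SAP 6.2. No scheduled rating is lost, because no post-baseline efficacy rating is planned for Day 1. If wanted for clarity, SAP 15.2.1.3 and 15.2.1.5 can say that Day 0 means the Baseline visit.

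The cost is a few words in the SAP before unblinding, with no effect on data collection. A blinded count of Top 3 Concerns baseline forms dated on the first-dose date would show p, and so whether the point has any effect in this trial.

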9.2 Study Population

9.2.1 Inclusion Criteria

The patient must meet all of the following inclusion criteria to be eligible for enrolment into the study:

Demographics

1. Female or male ≥ 4 years of age.
2. Body weight ≥ 10 kg, and within the expected range for an RTT patient, based on age and height.

Diagnostic

3. Diagnosis of Rett syndrome based on consensus clinical criteria (Neul et al, 2010; Appendix 4). A test for MECP2 mutations (Xq28) will be performed if results from an accredited laboratory are not available; selection for the trial is not contingent on the results of the MECP2 test. Patients with known MECP2 duplications will not be eligible.
4. One or more of the following breathing dysfunctions: periodic apnea during wakefulness; intermittent hyperventilation; breath holding spells; air swallowing; forced expulsion of air or saliva.
5. Patient meets all of the following criteria related to breathing abnormalities:
 - a. Parent report of 10 episodes or more of breathing abnormality per day during wakefulness in the week prior to the screening visit;
 - b. Time per hour spent on normal breathing is less than 90% of the total time per hour of wakefulness (i.e., $\geq 10\%$ of the time should be abnormal breathing);

- c. Has at least 10 episodes of breathing dysrhythmia, defined by episodes ≥ 10 seconds of breath holding (apnea), per hour, during cardiorespiratory monitoring (performed with home/ambulatory monitoring system during screening period).
6. Stable medication regimen for 4 weeks prior to beginning the study (if receiving services - physical, occupational, or speech therapy - subjects must be on a stable regimen of these services for 3 months prior to beginning the study). Female patients of childbearing potential are to use adequate contraception as recommended by their Health Care Provider (see [Section 13.1.8](#)).

Procedural

7. Parent/legal guardian/representative has provided written consent prior to the patient participating in the study. Where feasible, consent or assent for patients less than 18 years of age, has also been provided by the patient.
8. Ability to take study medication provided either as capsules or combined with food/drink.
9. Patient is cooperative, willing to complete all aspects of the study, and capable of doing so with assistance of a caregiver.
10. Caregiver is able to understand the instructions and fully participate.

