must meet all criteria related to breathing abnormalities in at least one of the three screening period assessments, as specified in the Inclusion Criteria, to be eligible for enrollment. If the patient meets the criteria, as determined by Vivonoetics, in any week of the Screening period, home monitoring in the subsequent week(s) of Screening would not be required. Adverse events and use of concomitant medication will be recorded from the time of signing of the consent form.

At the Baseline visit (Day 0), the inclusion/exclusion criteria, (respiratory inclusion criteria will be assessed based on home respiratory monitoring performed during screening) will be reviewed to ensure that the patient is suitable for enrolment. Patients meeting all entry criteria at baseline will undergo a series of evaluations on the day prior to dosing (Day 0). Baseline assessments of respiratory function will be performed in the clinic using a stretch-sensitive resistance plethysmograph (SOMNOtouch™ device), Tanner Staging will be performed, and a blood sample will be taken for measurement of serum prolactin, and plasma ACTH and cortisol. The routine laboratory tests and physical and neurological examinations do not need to be repeated if performed less than 28 days before baseline, unless abnormalities are noted that require follow-up. A routine ophthalmological examination (including visual acuity, lens, intraocular pressure and dilated examination of the fundus, and OCT, if feasible for the patient) will be performed. A serum pregnancy test must be performed for post-pubertal females. In addition, baseline assessments for all of the efficacy variables [respiratory measures, heart rate, Motor-Behavioral Assessment Scale, Caregiver Top 3 Concerns, and RCSS], as well as the suicidality assessment, will be performed on Day 0. Baseline vital signs and ECG evaluations will be performed in triplicate (10 min apart) on Day 0 or at least one hour prior to dosing on Day 1.

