The patient will return for the final scheduled visit at Week 24, or if they discontinue from the study prematurely. The caregiver should be instructed not to administer the morning dose of the study medication on the day of the Week 24 visit to the clinic, as patients who continue in the open-label extension treatment period will receive their first dose of study medication on this day. All final safety [vital signs, 12-lead ECG, laboratory tests (hematology, blood chemistry, urinalysis, and measurement of serum prolactin, and plasma ACTH and cortisol), Tanner Staging, and physical, neurological and ophthalmological examinations (including OCT, if feasible for the patient), and the suicidality assessment] and efficacy assessments [respiratory measures, heart rate, CGI-C, CIC, Motor-Behavioral Assessment Scale, Caregiver Top 3 Concerns, and RCSS] will be performed at this visit. The results from the Week 24 assessment of the primary efficacy measure of respiratory function (data from home respiratory monitoring on 3 days in the week preceding the visit), as well as all other secondary efficacy measures assessed during the visit, will be considered the endpoint value for statistical analysis purposes.

All patients who have completed the final evaluations at Week 24 (Day 168), have no safety or tolerability issues that would preclude continuing on the study medication, have been compliant with the trial requirements, and have not worsened to the extent that they are considered at an increased risk for morbidity or mortality, as judged by the Investigator, will be eligible to enter the initial 24-week, open-label, extension treatment period of the study. Patients who do not wish to continue treatment will have their study medication discontinued and will be asked to return for a safety follow-up visit 2 weeks after their final dose, during which vital signs and an assessment of adverse events will be performed. Any Serious Adverse Events (SAEs) occurring within 30 days after the final dose will be reported.

168-Week Open-label Extension Treatment Period

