12.2 Efficacy Assessments

12.2.1 Number of Apnea Episodes (Primary Efficacy Outcome)

Measurement of specific cardiorespiratory parameters for the assessment of primary and secondary efficacy outcomes during the initial 24-week treatment period will be performed at home using respiratory inductive plethysmography (RIP) coupled with the BioRadio™ wireless physiological monitor (Great Lakes Neurotechnologies, Cleveland, Ohio). A brief description of RIP and use of the BioRadio is provided in [Appendix 5](#). The cardio-respiratory data collected using the BioRadio will be analysed and summarized by an external vendor, Vivonoetics. A description of the analysis plan and procedures will be provided in a separate document.

The primary efficacy measure to be used in assessing the efficacy of sarizotan in treating the respiratory symptoms associated with RTT will be the percent reduction (change) from baseline in the number of apnea episodes (each ≥ 10 seconds in duration) per hour, during awake time, from baseline to endpoint (Week 24 or early discontinuation). This will be calculated from the data obtained during home respiratory monitoring.

Home cardiorespiratory monitoring will be performed during the screening period (three 3-day test periods during first 3 weeks) and for 3 days in the week prior to each scheduled clinic visit at Weeks 2, 8, 16 and 24. Monitoring will be performed when the patient is awake for 6 hours on each of the 3 days. Data from all of the quality recording time (minimally 3 hours) in the Screening period and from the week prior to each of the visits at Weeks 2, 8, 16 and 24 will be averaged and used in calculating the value for the primary efficacy measure. If the patient meets the criterion for number of apnea episodes, as determined by Vivonoetics, in any week of the Screening period, home monitoring in the subsequent week(s) would not be required, and the screening data would be used to calculate the baseline value for the analyses.

The caregiver should perform the home monitoring starting at approximately the same time each day. If the patient attends school, the monitoring should be performed when the patient is at home, if at all possible; otherwise, it should be noted when the monitoring is performed at school.

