15.2.6 Efficacy evaluations

Primary Efficacy Outcome

The primary efficacy outcome will be the percent reduction (change) from baseline in the number of apnea episodes (each ≥ 10 seconds in duration) per hour, during awake time. This will be calculated from the data obtained during home respiratory monitoring by means of an ambulatory data acquisition system (BioRadio™) designed to record specific respiratory and cardiac parameters. Assessment of the respiratory outcomes will be performed at home on any 3 days in each of the first 3 weeks of the Screening period, and in the week prior to each of the visits at Weeks 2, 8, 16, and 24. Monitoring will be performed when the patient is awake and should be attempted for 6 hours on each of the 3 days. Data from all of the quality recording time (minimally 3 hours) in the Screening period, and from the week prior to each of the visits at Weeks 2, 8, 16, and 24, will be averaged and used in calculating the value for the primary efficacy measure. If the patient meets the criterion for number of apnea episodes, as determined by Vivonoetics, in any week of the Screening period, home monitoring in the subsequent week(s) would not be required, and the screening data would be used to calculate the baseline value for the analyses.

The primary efficacy analysis for the initial, 24-week, double-blind, treatment period will be performed on the Intent-to-Treat (ITT) population, consisting of all patients who were randomized to treatment. The percent reduction (change) from baseline in the number of apnea episodes (each ≥ 10 seconds in duration) per hour will be compared between treatment groups using a Mixed Model Repeated Measures (MMRM) analysis. The MMRM model will include percent change from baseline as response, the fixed, categorical effects of treatment group, visit, treatment group-by-visit interaction, and the continuous terms age and baseline value as covariate. A statistically significant difference between high dose sarizotan (5 or 10 mg *bid*) and placebo will be considered evidence of efficacy in reducing apnea.

Key Secondary Efficacy Outcome

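### SAP 8.2 takes the last BioRadio value before Day 1 as baseline where the protocol averages all quality screening time, and the SAP neither lists the change nor says what one value is

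*SAP*

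**What the plan says.** **Protocol.** Section 15.2.6 gives the aggregation rule for the primary measure, and the synopsis and 12.2.1 repeat it. It takes "Data from all of the quality recording time (minimally 3 hours) in the Screening period", together with the week before each visit, and says these "will be averaged and used in calculating the value for the primary efficacy measure". When a patient meets the apnea criterion in one screening week, later weeks need not be recorded, and "the screening data would be used to calculate the baseline value for the analyses".

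**SAP.** The visit-window table in 8.2 has an instruction for this device alone: "Baseline for the BioRadio™ data will be the last value prior to Day 1 (no cutoff at Day -28". Below the table, 8.2 says that when a window holds several records, the one nearest the scheduled day is kept. SAP 15.1.1 gives the outcome and the recording schedule and names the vendor as the data source. It has no averaging step, no 3-hour minimum and no definition of a record. SAP 3.3 reports no changes from the protocol.

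**Vendor.** Protocol 12.2.1 says: "The cardio-respiratory data collected using the BioRadio will be analysed and summarized by an external vendor". It places the details in a separate document, which the SAP does not cite.

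**The concern.** The last of several values and the average of all of them are different baselines. Baseline enters the primary analysis twice: as the denominator of the percent change (SAP 6.5) and as a covariate in the MMRM (SAP 15.1.3). If the vendor file holds more than one screening value per patient, the same recordings support two different primary variables, one under each document. The SAP discloses no departure. Its planned supportive analyses (per-protocol population, outliers included) do not vary the baseline. A programmer could not rebuild the primary variable from the SAP alone.

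Screening also gives the choice a direction. Inclusion criterion 5c requires that the patient "Has at least 10 episodes of breathing dysrhythmia" per hour, and protocol 11.2 says the patient "must meet all criteria related to breathing abnormalities in at least one of the three screening period assessments". Suppose records are weekly, a patient was kept in screening because the apnea count was too low, and monitoring then stopped. The last week is the qualifying week and the earlier ones were below 10 per hour. For such a patient the last value lies above the average of all screening weeks, and the apparent reduction at Week 24 is larger.

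**Working it through.** **1. What the plan's figures can settle.** No figure in the plan depends on the baseline rule. The planned sample size reproduces: a two-group t-test with a 10-point difference, SD 12.5, two-sided alpha 0.05 and 34 per group has 90.2% power. It does not help to choose between the rules, because the documents give no within-patient variability.

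**2. When the two baselines differ.**

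| Vendor record | Usable screening data | Do the rules agree? |
|---|---|---|
| One pooled screening average | any | yes |
| Weekly averages | one week only | yes |
| Weekly averages | several weeks, protocol read as the qualifying week only, monitoring stopped there | yes |
| Weekly averages | several weeks, protocol read as all weeks | no, unless the values coincide |
| Daily values | more than one day | no, unless the values coincide |

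The third row exists because protocol 15.2.6 averages the screening data and then refers to using the screening data once a week qualifies. It does not say whether that means every recorded week or the qualifying week.

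**3. Size in a single patient.** The formula in SAP 6.5 is 100 x (visit value - baseline) / baseline. The weekly values below are invented. They assume equal quality hours in each week and a Week 24 value of 10 per hour.

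- Weeks at 8, 9 and 14. Average: (8 + 9 + 14)/3 = 10.33, so (10 - 10.33)/10.33 = -3.2%. Last value: (10 - 14)/14 = -28.6%.
- Weeks at 9 and 12. Average: 10.5, so (10 - 10.5)/10.5 = -4.8%. Last value: (10 - 12)/12 = -16.7%.
- In general, let the visit value be 0.9 times the screening average (a -10% change) and the last value 1.125 times that average. The last-value rule then gives 0.9/1.125 - 1 = -20%.

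**4. The averaging itself needs defining.** Take the weeks at 8, 9 and 14 with 18, 18 and 3 quality hours (18 is 3 days of 6 hours as attempted; 3 is the stated minimum). Total episodes over total hours is (8 x 18 + 9 x 18 + 14 x 3)/39 = 348/39 = 8.92. The change is (10 - 8.92)/8.92 = +12.1%. This comes from the protocol's unspecified weighting, not from the mismatch with the SAP, but the same SAP sentence has to resolve it.

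**5. Post-baseline values.** Protocol 11.2 bases the Week 24 value on "data from home respiratory monitoring on 3 days in the week preceding the visit". The nearest-record rule discards part of that set only if records are daily. With one averaged record per recording week, it merely chooses between sets.

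**The case against.** The strongest reply is that the documents can be read as consistent. The vendor summarizes the recordings, so a value in SAP 8.2 may already be the vendor's average. SAP 8.2 is a windowing table that picks among delivered records, and what its BioRadio note mainly adds is that screening recordings older than Day -28 are kept. On that reading SAP 3.3 is correct. The nearest-record rule proves little, because the analysis windows run for weeks and a tie-break is routine. Many patients may also be unaffected. With weekly records, anyone who qualified in week 1 and stopped has one value, and week 1 also serves to resolve recording problems, so some patients may have only one usable week.

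All of that limits the size of the problem. It does not remove it: no passage says that the vendor sends one pooled value, and the words in SAP 8.2 state a different rule from the protocol's.

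Three stronger readings are tempting and not supported:

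- **That the sponsor departed from the protocol without saying so.** The text shows a mismatch, not which derivation was used.
- **That the last-value rule biases the treatment comparison.** The baseline is fixed before randomization and affects all arms alike, so it does not create a difference where there is none. The 10-point shift in the third example equals the planned arm difference in size, but it is a shift in one patient.
- **That power falls materially.** A loss can be calculated only by assuming single-day records and a share of the variance due to day-to-day noise. The documents give neither, and the loss may be nil.

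**Conclusion.** The point stands as a conflict of wording on the primary variable. It is certain that SAP 8.2 and the protocol state different baseline rules, that SAP 15.1.1 omits the averaging and the 3-hour minimum, that no record unit is given, and that SAP 3.3 lists no change.

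The numerical consequence is conditional on the vendor record. It is nil with one pooled screening average per patient, or with weekly values and a single usable week. With several screening values per patient it can be large for an individual, as the 25-point gap between -3.2% and -28.6% shows. That example assumes weekly records, equal hours and all screening weeks counted; under the qualifying-week reading both rules give -28.6%. The number of patients affected cannot be obtained from the documents.

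The matter should be settled before unblinding because it concerns precision and the need for one pre-specified primary variable.

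**What to change.** Before unblinding, in this order:

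1. Confirm with the vendor whether a record is a day, a week or the whole screening period. State this in SAP 15.1.1 and cite the vendor's derivation document.
2. In SAP 8.2 and 15.1.1, define the BioRadio baseline as total apnea episodes divided by total quality hours over all recorded screening weeks, with at least 3 quality hours in the set. Say how a set below that minimum is handled. Keep the exception to the Day -28 cutoff so that early screening recordings are not lost.
3. Define each post-baseline value the same way over the week before the visit. Let the nearest-record rule choose only between whole averaged recording sets in one window.
4. If the last value or the qualifying week is the intended baseline, list it in SAP 3.3 with a reason and run the all-screening average as a sensitivity analysis.

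If step 1 shows one pooled value per patient, clarifying the wording is enough, provided the pooled value follows the definition in step 2.

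The cost is SAP text and derivation code. The recordings already exist; the vendor may have to resend episode counts and quality hours. No protocol amendment is needed for this alone, and the wording of protocol 15.2.6 can be aligned at the next one.
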